### **2.2.1 Subgroup of interest**

Not Applicable.

## **2.3 Subject disposition, demographics and other baseline characteristics**

### **2.3.1 Subject disposition**

Subject disposition will be summarized separately by treatment group and in total for the All-Enrolled Set: the number and percentage of screen failures (including the primary reason for screen failure), subjects enrolled, randomized, randomized and treated with GT005, completed study, discontinued the study prematurely (including the primary reason for premature study discontinuation).

A listing of subjects who discontinued study earlier than the planned end-of-study will be provided by treatment group for the FAS. This listing will identify the last visit completed and when the study was discontinued including the primary reason.

In addition, protocol deviations (PDs) will be listed and summarized by the number and percentage of subjects with each deviation category for the FAS.

### 2.3.2 Demographics and other baseline characteristics

Demographic and baseline characteristics including age, race, (self-reported and genetically defined) ethnicity, sex, and AMD genetic subgroup will be summarized with descriptive statistics or counts and percentages of subjects as appropriate by treatment group and in total for FAS.

Summary statistics will be presented for the study eye if they are baseline ocular characteristics. Listings for demographic and ocular baseline characteristics will be provided.

Baseline ocular characteristics for the study eye will be summarized by treatment group and in total for the FAS. Ocular baseline characteristics include:

- Study eye selection (left eye OS or right eye OD)
- Best corrected visual acuity BCVA (in ETDRS letters)
- Low-luminance visual acuity (LLVA) (in ETDRS letters)
- Low luminance deficit (LLD) (BCVA - LLVA in ETDRS letters)
- GA lesion area (mm^2) as assessed by FAF
- GA contour (Unifocal, Multifocal, Cannot Grade) as assessed by FAF
- GA foveal involvement (Foveal, Non-foveal, Cannot Grade) as assessed by FAF and optical coherence tomography (OCT)
- Junctional zone pattern (Atypical, Banded, Diffuse, Focal, Cannot Grade) as assessed by FAF
- Presence of hard drusen (Yes, No, Cannot Grade) as assessed by color fundus photography (CFP)
- Presence of soft drusen (Yes, No, Cannot Grade) as assessed by CFP
- Presence of calcified drusen (Yes, No, Cannot Grade) as assessed by CFP
- Presence of cuticular drusen (Yes, No, Cannot Grade) as assessed by CFP
- Presence of subretinal hemorrhage (Yes, No, Cannot Grade) as assessed by CFP
- Presence of intraretinal hemorrhage (Yes, No, Cannot Grade) as assessed by CFP
- Presence of reticular pseudodrusen (Yes, No, Cannot Grade) as assessed by OCT
- Central Subfield Thickness (CSFT) (μm) as assessed by OCT
- Years since GA diagnosis

### 2.3.3 Medical history

Medical histories/current medical conditions will be listed by treatment arm, including the reported term/PT/SOC, laterality if applicable, start/end date, ongoing status (Yes, No) indicating whether the event is ongoing by the time of analysis, etc. These outputs will be based on the FAS.

## **2.4 Treatments (study treatment, rescue medication, concomitant therapies, compliance)**

### **2.4.1 Study treatment**

The FAS will be used for the analyses below.

GT005 is administered as a single-time subretinal injection into the study eye of subjects allocated to one of the two GT005 doses. The surgical procedure for subretinal administration of GT005 is based on a standardized methodology. It is conducted by an appropriately qualified Vitreoretinal Surgeon in an operating room under appropriate anesthesia. Subjects allocated to the untreated control will not receive any treatment.

Study treatment will be summarized by the number and percentage of subjects randomized, subjects underwent study surgery, subjects treated with GT005, subjects who did not complete the study surgery successfully (including the primary reason for preventing successful completion of surgery, related/unrelated to the surgery procedure). The number and percentage of subjects discontinued study prior to surgery (including the primary reason for discontinuation) will also be provided.

A listing for surgical and dose administration records will be provided.

### **2.4.2 Prior, concomitant and post therapies**

Prior medications are defined as drugs taken and stopped prior to the date of randomization. Any medication given at least once between the date of randomization and the last study visit will be a concomitant medication, including those that were started pre-baseline visits and continued into the treatment period. Prior or concomitant medication will be identified based on recorded or imputed start and end dates of taking the medication.

Prior and concomitant medications will be coded according to the WHO Drug Reference List dictionary with Anatomical Therapeutic Classification (ACT) class and preferred term (PT).

Concurrent procedures will be summarized by treatment group and in total for ocular (study eye and fellow eye) and non-ocular events, presented with the number and percentage of patients by System Organ Class (SOC) and PT.

Prior medications and concomitant medications will be listed by treatment arms, including the reported name of medication/standardized medication name, indication, route of administration, laterality if applicable, start/end date, etc.

## **2.5 Analysis supporting primary objective(s)**

The primary objective of this study is to evaluate the effect of GT005 vs untreated control on the progression of GA in subjects with GA due to AMD. This will be evaluated by measuring the GA area over time using FAF.

### **2.5.1 Primary endpoint(s)**

The primary endpoint is the change from baseline to Week 48 in GA area as measured by FAF.

### **2.5.2 Statistical hypothesis, model, and method of analysis**

The primary endpoint will be estimated among treatment groups via least-squares means from a mixed model repeated measures (MMRM) analysis. The model will include the change from baseline in GA area measured by FAF as the dependent variable, GA area at the baseline as the covariate, assessment visit, treatment group, three interaction terms (assessment visit and treatment group, assessment visit and GA area at the baseline, GA area at the baseline and treatment group) as the fixed effect and subject as a random effect.

An unstructured within subject correlation structure will be used for the covariance matrix. If the unstructured covariance matrix results in a lack of convergence then other covariance structures will be investigated. Toeplitz, First Order Autoregressive AR(1), and Compound Symmetry will be applied, in the specified order, until the model converges.

The estimated least-squares mean (LSM) for the change in GA area, and treatment difference of each GT005 dose against untreated control, as well as the corresponding 90% confidence interval, will be summarized by visit and treatment groups. A line plot for the estimated LSM with 90% CI by visit and treatment groups will also be provided.

As this study is being terminated, statistical modeling as described above and/or summary tables will be provided as appropriate based on data availability.

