V6.0, 06 DEC 2022	
 
Study design has been amended so that Part 1 provides an evaluation of CFI rare variant GA subjects with the low and high dose of GT005 compared with untreated control, and Part 2 evaluates the broad genetic GA population with the low dose of GT005 compared with untreated control. The overall study sample size has been increased to approximately 202.
 
	
 
In its current form, the study is unlikely to achieve enrolment, and therefore its overall scientific objective, in a reasonable timeframe. This is due to challenges encountered in recruiting GA patients with a CFI rare variant genotype, which accounts for approximately 3% of the overall GA population. Hence the study has been adjusted to include Part 2 with a more recruitable population of GA patients with a broad genetic background. The modification of the study population is justified based on emerging data which strengthens the hypothesis that complement-targeted therapies have potential to treat a genetically broad GA population. With this amendment, the primary objective of the study remains unchanged; subjects will continue to be genotyped as part of the screening assessments for the study, and analysis of the effect of GT005 according to genetically defined subgroups (including the original population of CFI rare variants) is still planned
 

Protocol Version	Change	Justification
	
 
Updated Study Objectives in Synopsis and Section 2 secondary [REDACTED] to be reported through Week 96
 
	
 
Clarified the analysis timepoints for secondary [REDACTED] to be reported until the end of study
 

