**Determination of Study Eye:**

In Part 1 and Part 2, the eye with the worse visual acuity will be selected as the study eye. If visual acuity is equivalent in both eyes, the eye with the largest area of GA will be the study eye unless the subject (in consultation with the Surgeon) expresses an alternative preference. The study eye will be confirmed by the Vitreoretinal Surgeon. [REDACTED]

[REDACTED]. A permuted-block method will be used to obtain an approximately 2:1 ratio between the treatment group(s) and control within each part of the study within each stratum. [REDACTED]

Following randomisation, the Investigator will be informed of the subjects' allocated treatment assignment (i.e., treatment with GT005 or the untreated control group, but not the GT005 dose group) and the study eye selected. In Part 1, the Sponsor, Investigators, subjects, and study personnel performing clinical assessments will remain **dose-masked** to dose received for those randomised to GT005. In Part 2, the Sponsor, Investigators, subjects, and study personnel performing clinical assessments will be **unmasked** to the treatment arm (GT005 or untreated control) and therefore dose, since only the low dose will be administered. To minimise bias, all imaging endpoint assessments and grading will be performed at a Central Reading Centre (CRC). All imaging efficacy assessments are to be performed in a fully masked fashion. [REDACTED]

Subjects screened at a local investigative site who are randomised to GT005 may undertake a visit to the surgical site between the screening and pre-surgery visit in order to meet the surgical team and discuss the procedure.

Subject consent, screening and confirmation of eligibility, and most follow-up visits will be conducted at either local or surgical investigative sites. Subjects allocated to GT005 will undergo subretinal surgery for the administration of GT005. [REDACTED]

[REDACTED] For women of childbearing potential, a second pregnancy test will be performed at Visit 2. GT005 is administered as a single-time subretinal injection into the study eye. [REDACTED]

[REDACTED]. Post-dosing ophthalmic and clinical assessments will be performed as described in [Table 1; Table 2]. Visits 2 to 5 will be performed for subjects randomised to GT005, as described in [Table 1; Table 2].

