### **2.5.4 Handling of missing values not related to intercurrent event**

In the case of missing data occurring in other scenarios, i.e. independent of intercurrent events defined in [Table 1-2](#), the estimand based on an MAR approach will be considered specifically for each treatment arm the subjects are assigned.

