### **2.5.5 Sensitivity analyses**

Not applicable.

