- The change in BCVA through Week 96 will be estimated among treatment groups via least squares means from a MMRM model. The model will include the change from baseline in BCVA measured by ETDRS as the dependent variable, BCVA at the baseline as the covariate, assessment visit, treatment group, two interaction terms (assessment visit and treatment group, assessment visit and BCVA at the baseline) as the fixed effect and participant as a random effect. The estimated least-squares mean (LSM) for the change in BCVA, and treatment difference against untreated control, as well as the corresponding 90% confidence interval, will be summarized by visit and treatment groups. A line plot for the estimated LSM with 90% CI by visit and treatment groups will also be provided. All BCVA assessments will be listed by treatment group, site, and subject.

4.b Change in low luminance difference (LLD) via the ETDRS chart through Week 96

- The LLD and the changes from baseline will be summarized based on observed data by assessment visits and treatment group. All LLD assessments will be listed by treatment group, site, and subject.

5.a Change in reading performance as assessed by Minnesota low-vision reading test (MNRead) chart through Week 96

- The Maximum reading speed (MRS) for each eye as assessed by MNRead Chart and the change from baseline will be summarized based on observed data by visit and treatment group. Reading speed (words per minute) will be computed for each of the 19 sentences read using the following formula:
$$60 \times \max(0, 10 - \text{number of errors}) / \text{reading time in seconds}$$
The mean of three higher reading speeds will be reported as the maximum reading speed.

### 5.b Change in functional reading independence (FRI) index through Week 96

- The FRI index and the changes from baseline will be calculated and summarized based on observed data by assessment visits and treatment group.

6. Change in quality of life measured on the visual function questionnaire-25 (VFQ-25) through Week 96

- The VFQ-25 sub-scales and composite scores and the changes from baseline will be calculated and summarized based on observed data by assessment visits and treatment group.

As this study is being terminated, statistical modeling and/or summary tables for corresponding endpoints will be provided as appropriate based on data availability.

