### 5.4 Statistical models

#### 5.4.1 Analysis supporting primary objective(s)

The following MMRM will be used for the primary efficacy endpoint. The model will include the change from baseline in GA area measured by FAF as the dependent variable, GA area at the baseline as the covariate, assessment visit, treatment group, two interaction terms (assessment visit and treatment group, assessment visit and GA area at the baseline) as the fixed effect and participant as a random effect.

For this analysis, the data structure is one record per subject per scheduled visit. The data will include all subjects and have records for all scheduled visits, regardless of whether the assessment was missed or not at a given visit. Missing values will not be imputed and will be passed to the model as missing. The SAS PROC MIXED will be used to perform the analysis.

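### The high dose, randomised only in Part 1 among CFI rare-variant carriers, is compared with controls pooled over both Parts, and no readable analysis gives the Part 1 comparison

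*SAP*

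**What the plan says.** Randomisation is organised by Part. The Protocol Synopsis (Determination of Study Eye) aims for an "approximately 2:1 ratio between the treatment group(s) and control within each part of the study within each stratum". Part 1 takes only carriers of CFI rare variants linked to low serum CFI; Part 2 takes any genotype and opens after Part 1 closes (Protocol Synopsis, Study Population; SAP 1.1). Part 2 offers low dose or control only. Protocol 9.1 and SAP 3 put the high-dose group at about 10 subjects, all from Part 1.

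The analysis is not organised by Part. Both documents state the two dose hypotheses against a pooled untreated control. SAP 2.1.1.1 has one control group, and SAP 2.2 puts all randomised subjects in the Full Analysis Set. The primary MMRM in SAP 2.5.2 includes "GA area at the baseline as the covariate, assessment visit, treatment group, three interaction terms". SAP 5.4.1 describes the same model with "two interaction terms (assessment visit and treatment group, assessment visit and GA area at the baseline". The two descriptions disagree on the interactions, which is a separate matter, but neither has a term for Part or genotype. The BCVA model in SAP 2.6.2 has "BCVA at the baseline as the covariate, assessment visit, treatment group, two interaction terms" and likewise no Part term.

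SAP 2.5.5 on sensitivity analyses reads "Not applicable". Sections 2.2.1 (subgroups) and 2.5.6 (supplementary analyses) say the same. Genetic subgroup appears only as a baseline summary (SAP 2.3.2). SAP 2.5.2 and 2.6.2 both add that, because of termination, modelling or summary tables will be produced as the data allow.

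**The concern.** A Part 2 control could never have been allocated to the high dose. For that contrast, such controls are non-concurrent and come from a different population. Protocol V6.0 says of the rare-variant genotype that it is one "which accounts for approximately 3% of the overall GA population". If Part 2 recruitment is unselected, 10 Part 2 controls would include about 0.03 × 10 = 0.3 carriers, whereas every high-dose subject is a carrier. The true number may be higher, because rare-variant subjects are directed to Part 2 once Part 1 closes.

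If untreated GA growth differs between the Parts after adjustment for baseline GA area, part of that difference will be reported as a high-dose effect. The low-dose and high-dose rows of the results table also describe different populations. Protocol 1.5.2 raises the possibility that rare-variant subjects respond more, so a reader could mistake a population difference for a dose response.

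**Working it through.** **The plan's own figure.** The total of about 202 cannot be reproduced uniquely, because target effect and power are blacked out. One set of assumptions that fits is a 25% reduction (0.25 × 2.1 = 0.525 mm²), 80% power, one-sided 0.05, SD 1.3 and 2:1 allocation. Controls = 1.5 × (1.645 + 0.842)² × 1.3² / 0.525² = 57; evaluable = 3 × 57 = 171; after 10–12% loss 190–195; plus 10 high dose = 200–205. A 30% reduction at 90% power also fits (196–198 at 11–12% loss). Nothing below depends on this choice.

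**Inputs.** From the documents: about 10 high-dose subjects, SD 1.3 mm² at Week 48, 90% CI. Assumed: 10 Part 1 controls (2:1 with an equal dose split gives 10/10/10), Part 2 controls n₂ = 2, 5 or 10, and a residual Part difference D in untreated growth of 0 to 0.5 mm².

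**Formulas** (complete data at the visit).
- Share s = n₂/(10 + n₂); bias b = s × D
- Pooled SE = 1.3 × √(1/10 + 1/(10 + n₂)); half-width = 1.645 × SE
- Coverage = Φ(1.645 − b/SE) − Φ(−1.645 − b/SE)

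| Part 2 controls | Share | Largest bias (D = 0.5) | Pooled SE | Half-width | Bias / half-width | Coverage |
|---|---|---|---|---|---|---|
| 2 | 2/12 = 0.167 | 0.08 | 0.557 | 0.92 | 9% | 89.6% |
| 5 | 5/15 = 0.333 | 0.17 | 0.531 | 0.87 | 19% | 88.3% |
| 10 | 10/20 = 0.500 | 0.25 | 0.503 | 0.83 | 30% | 85.8% |

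Larger shares are worse. Had the study filled, Part 2 would have had (202 − 30)/3 = 57 controls: share 57/67 = 0.85, bias up to 0.43 mm², coverage about 75%.

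**Part 1 only.** SE = 1.3 × √(1/10 + 1/10) = 0.581; half-width 0.96 mm².

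**Low dose.** This arm also spans both Parts, so most of D cancels. With Part 2 low/control of 10/5, the shift is (5/15 − 10/20) × D = −0.167 × D, at most 0.08 mm² in size; 20/10 gives the same.

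**Few Part 2 controls at Week 48 does not settle it.** SAP 5.4.1 says "Missing values will not be imputed and will be passed to the model as missing", and under SAP 2.5.4 "the estimand based on an MAR approach will be considered specifically for each treatment arm". Part 2 controls with early visits only therefore still inform the Week 48 control mean through the within-subject covariance. How much depends on a covariance that the documents do not give.

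**The case against.** The pooled control is a declared choice, stated openly as the reference in the protocol and written into both hypotheses. The study is exploratory and being terminated, and the data-availability clause means the high-dose model may never be fitted. All of that stands and limits the weight of the point. Declaring the pool does not, however, remove the confounding.

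The strongest objection is about precision. On mean squared error, Part 1 only beats pooling when D exceeds √(0.581² − SE²)/s, which is 1.01, 0.71 and 0.58 mm² for 2, 5 and 10 Part 2 controls. All three lie above the assumed 0.5. Nor is the comparison a useful test of pooling. The SE of the gap between the two estimates is 1.3 × √(1/10 − 1/(10 + n₂)) = 0.17, 0.24 and 0.29, so the largest assumed bias would be detected at two-sided 10% only about 14%, 18% and 22% of the time. This stands in full. It is why the primary model should stay, and why the added analysis should be described as the randomised estimate set beside the pooled one.

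The premise is also partly unobserved. No passage shows that a Part 2 control was randomised, or that untreated growth differs by CFI genotype or enrolment period. Stratification factors and some SAP sections are blacked out and may contain an analysis by Part or genotype, although SAP 2.2.1 and 4 point the other way.

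**Conclusion.** The point holds as a matter of interpretation. In the readable SAP, the high dose is never compared with its own randomised controls alone, and the planned contrast can be partly confounded with Part. Confounding is partial, because Part 1 controls are in the pool and baseline GA area is adjusted for. Size and direction are unknown. The range of 0.08 to 0.25 mm² and coverage of 89.6% to 85.8% are worst cases within assumed counts and an assumed difference of up to 0.5 mm².

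A reader might infer that the high-dose result is biased in favour of GT005, or is invalid. The documents do not support either: they give no untreated growth rate by Part and no control counts by Part. A reader might also infer that the SAP contradicts the genetic subgroup analysis mentioned in the V6.0 amendment history. It does not: SAP 4 lists the absence of subgroups as a change from the protocol. No decision rule depends on this contrast.

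**What to change.** Leave the primary model as it is. In SAP 2.5.5, replace the present entry with a comparison of high dose against Part 1 randomised controls. Fit it to Part 1 subjects only, so that early Part 2 visits do not enter. Report the LSM difference with 90% CI by visit, or a descriptive summary if the data do not support a model, consistent with the clause in SAP 2.5.2 and 2.6.2. Do the same for BCVA.

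Beside the primary table, give control counts by Part at each visit. State that the high-dose result applies to the rare-variant population and is not directly comparable with the low-dose result.

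An additive Part term is not an equivalent substitute: it assumes the same low-dose effect in both Parts, which Protocol 1.5.2 gives reason to doubt.

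Cost: SAP wording, one extra table per endpoint and one row of counts. The drawback is a wider interval, with a half-width of about 0.96 mm² against 0.83 to 0.92 pooled. The SAP should say that, at these sizes, the comparison cannot reliably show whether pooling drives the result. If a blacked-out section already contains it, a cross-reference is enough.

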[REDACTED]

[REDACTED]

Subsequent follow-up visits at Weeks 12, 24, 36, 48, 72, and 96 (Visits 6, 7, 8, 9, 10, and 11) will be conducted for both GT005 and untreated control subjects at the local investigative or surgical sites. Visit 11 will be during the Week 96 (end of study visit). If a subject drops out, or is withdrawn from the study, every reasonable effort will be made to complete the assessments scheduled for the Early Termination Visit.

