### 9.3 Significance Testing and Estimations

Type 1 error (alpha) is set at 0.05 one-sided and estimates of outcome parameters will be accompanied by 90% confidence intervals to be consistent with the Type 1 error level. No multiplicity adjustment will be applied since this is an exploratory study.

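### The primary MMRM pairs a random subject effect with an unstructured covariance: redundant if coded literally, and tied to a convergence rule that could then change the covariance for no data reason

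*SAP*

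**What the plan says.** SAP 2.5.2 describes the primary model for change in GA area by its dependent variable, baseline covariate, visit, treatment and interactions, "as the fixed effect and subject as a random effect". The next paragraph adds: "An unstructured within subject correlation structure will be used for the covariance matrix". It then gives a rule: "If the unstructured covariance matrix results in a lack of convergence then other covariance structures will be investigated". The order is fixed: "Toeplitz, First Order Autoregressive AR(1), and Compound Symmetry will be applied, in the specified order, until the model converges".

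SAP 5.4.1 restates the primary model "as the fixed effect and participant as a random effect" and names the software: "The SAS PROC MIXED will be used to perform the analysis". It names no covariance structure. SAP 2.6.2 applies the 2.5.2 model to GA area through Week 96 (item 1). For BCVA (item 4.a) it repeats the random participant effect but gives neither a covariance structure nor a fallback sequence.

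Nowhere does the SAP give RANDOM or REPEATED code, say whether the random effect is a separate intercept, or define lack of convergence.

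**The concern.** A random subject intercept adds the same constant to every variance and covariance within a subject. An unstructured matrix can already hold any such constant, so the data cannot divide it between the two. A programmer who follows the words would write both a RANDOM and a REPEATED statement and obtain an over-parameterised model.

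That would be only untidy if the SAP did not make the covariance structure depend on convergence. As written, a numerical stop caused purely by the redundancy could be read as grounds for leaving the unstructured model. The first fallback, Toeplitz, has the same redundancy, so the sequence could pass through it and settle on AR(1) plus intercept. Because lack of convergence is undefined, whether a singular Hessian or a covariance-matrix warning counts would be judged with the data in hand. SAP 2.5.5 plans no sensitivity analysis that would show the effect of the structure finally used.

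**Working it through.** The documents give no figure for the covariance model, so there is none to reproduce.

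**Inputs.** Protocol 3.1 has "Subsequent follow-up visits at Weeks 12, 24, 36, 48, 72, and 96" for both arms: six post-baseline visits, four of them up to Week 48. GT005 subjects also have FAF at Week 5 (Protocol Table 1), making seven. The SD of the Week 48 change is 1.3 mm² (SAP 3). Growth pattern and follow-up are not in the documents and are assumed below.

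**1. Identifiability.** The marginal covariance is V = σ_b²·J + R, with J a matrix of ones. If R is unstructured, replacing (σ_b², R) by (σ_b² + c, R − c·J) leaves V unchanged for any c that keeps both valid. R has T(T+1)/2 parameters, so:

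| Structure plus random intercept | Visits | Parameters | Rank |
|---|---|---|---|
| Unstructured | 4 | 10 + 1 = 11 | 10 |
| Unstructured | 6 | 21 + 1 = 22 | 21 |
| Unstructured | 7 | 28 + 1 = 29 | 28 |
| Toeplitz | 6 | 6 + 1 = 7 | 6 |
| Compound symmetry | 6 | 2 + 1 = 3 | 2 |
| AR(1) | 6 | 2 + 1 = 3 | 3 |

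Toeplitz absorbs c in every band and compound symmetry in its common covariance. AR(1) cannot. With V₀, V₁ and V₂ the covariances at lags 0, 1 and 2, V₀ − V₁ = σ²(1 − ρ) and V₁ − V₂ = σ²ρ(1 − ρ). Their ratio gives ρ, and then σ² and σ_b² follow.

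**2. Does the redundancy change the answer?** Fixed-effect estimates and their SEs depend on V only, and V is unaffected. REML was run on eight simulated data sets (assumed: 192 subjects, 2:1, four visits to Week 48, about 12% dropout, 25% effect):

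- Unstructured alone converged in 8/8.
- Unstructured plus intercept had a singular information matrix in every fit. Plain Newton stopped in 8/8.
- Generalised-inverse, ridge and bounded active-set steps converged in 8/8. The Week 48 difference and SE matched unstructured alone to within 3×10⁻⁶ (first data set: −0.5983, SE 0.2033).
- Steps that bounded the variance at zero without active-set handling reached the iteration limit in both data sets tried.

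So whether the fallback rule fires depends on the optimiser and the coding. PROC MIXED was not run.

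**3. What if the analysis reached AR(1) plus intercept?** Then V_jj = σ_b² + σ² at every visit. If change is driven by subject-specific linear growth with SD 1.3 at Week 48, the SD is 1.3 × 12/48 = 0.325 at Week 12 and 1.3 × 96/48 = 2.6 at Week 96. One common variance cannot fit these. Reported SE divided by true SE:

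| Assumed follow-up | Week 48 | Week 96 |
|---|---|---|
| 30 subjects to Week 96, 60 followed 12–56 weeks, 400 runs | 0.88 (90% CI covers 86%) | 0.44 (covers about 50%) |
| Same scenario, separate 200 runs | 0.86 (covers 86%) | 0.45 (covers 55%) |
| Complete data | 1.1 to 1.3 | about 0.7 |

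Unstructured alone, in the incomplete scenario, gave ratios of about 1.0 (Week 48) and 0.96 (Week 96) with coverage near 90% in 120 runs. A smaller set of 50 runs using normal quantiles gave ratios of 0.86 to 0.90 and coverage of 82% and 86%. That result is noisy, but shows no collapse at Week 96.

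**The case against.** The strongest reply is that nothing need go wrong. The SAP calls the analysis an MMRM and speaks of a single within-subject covariance matrix, so the random-effect phrase may be loose wording for the subject of the repeated measures. On that reading there is no defect. Even on the literal reading, a redundant parameter is not a convergence failure, and reaching AR(1) needs two failures in a row. All of this stands. It shows that harm is conditional, not that the text is sound: the wording permits two codings, one of them over-parameterised.

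A reader might infer that the SAP's own rule forces the primary analysis off the unstructured model. The documents do not support that. The trigger is lack of convergence, not non-identification; several optimisers reached the unstructured answer; and the named software was not tested.

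A reader might also infer that BCVA has the same defect. It does not as written: item 4.a of SAP 2.6.2 names no unstructured matrix, and a random participant effect alone is identified. Its gap is a different one, an unstated covariance structure.

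Finally, the study is being terminated after a futility analysis (SAP 1). Protocol 9.3 states "Type 1 error (alpha) is set at 0.05 one-sided", but Protocol 9.4.2 plans no inferential testing, and the SAP makes modelling conditional on data availability. The intervals are descriptive. This lowers the priority.

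**Conclusion.** The smaller claim holds. Coded literally, the SAP 2.5.2 model is over-parameterised by exactly one, as are two of its three fallbacks. That is algebra and rests on no data assumption. By itself the redundancy changes no estimate and no SE. The risk is a convergence stop unrelated to the data, followed by an undefined judgement that could end on AR(1) plus intercept.

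If that happened, the SEs would be wrong because equal variance is imposed on a measure whose spread grows with time. At Week 96 they were too small in every scenario tried (0.44 to about 0.7 of the true SE). It would be tempting to say that the Week 48 intervals would also be too narrow, but the direction there depends on follow-up: 0.86 to 0.88 with the assumed truncated follow-up, 1.1 to 1.3 with complete data. The subject counts, follow-up and linear growth are assumptions; the documents give only the SD and the planned total of approximately 202.

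This is a free improvement, not a must-fix.

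**What to change.** - **SAP 2.5.2 and 5.4.1:** delete the phrase that makes subject (or participant) a random effect. State a model with `REPEATED visit / SUBJECT=subject TYPE=UN` and no RANDOM statement. This is full rank (10 parameters at four visits, 21 at six).
- **Convergence rule:** apply it to that model only, and say what counts as non-convergence, including whether a singular Hessian does.
- **BCVA (SAP 2.6.2, item 4.a):** replace the random-effect phrase with the same repeated-measures unstructured specification and fallback. Deleting it alone would remove the only within-subject correlation stated there.

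The cost is a few lines of text before database lock. The intended model, the data and the sample size do not change. Toeplitz, AR(1) and compound symmetry as named still assume equal variance across visits, so that limitation would remain if the unstructured model failed for a genuine reason.
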